4.1. Demographics and Baseline Characteristics

The baseline measurement is defined as the closest measurement taken prior to the first study agent administration (Week 0) unless otherwise stated.

Subjects' demographic data including age, race, gender, height, weight, BSA, and BMI at baseline will be summarized. Baseline disease characteristics including duration of disease and baseline JIA efficacy assessments will be summarized.

Baseline TB information and medication usage will also be summarized.

The number of subjects will also be summarized by geographic region, country, and investigational site.

4.2. Disposition Information

The number of subjects screened, enrolled, and treated will be summarized. Subjects who discontinued study agent through Week 28, and 52, and 252, and the reasons for discontinuation will also be summarized. Likewise, subjects who terminated study participation and the reasons for termination will also be summarized.

4.3. Treatment Compliance

Subjects will be summarized by the study agent lot(s) received.

Treatment compliance will be assessed by summarizing the total number of infusions actually received, interrupted infusions, and incorrect ($\pm 15\%$ of calculated dose in mg) infusions.

4.4. Extent of Exposure

The cumulative dose of golimumab (mg/m²) and MTX dose (mg and mg/week) received will be summarized through Week 28, 52 and 252. The length of infusions will be summarized and subjects with <20 and >40 minutes infusion durations will be listed.

The number of administrations will be summarized.

The average follow-up time will also be summarized in the safety tables.

4.5. Protocol Deviations

Major protocol deviations will be tabulated separately and presented for the following categories:

- Subjects who entered the study but did not satisfy entry criteria,
- Subjects who received the incorrect dose
- Subjects who received disallowed medication, and other.

Besides these major deviations, other deviations may be summarized. Subjects with protocol deviations in study agent administration will be summarized by type of deviations.

All protocol deviations will be summarized through Week 28, through Week 52, and through Week 252 for the full analysis set.

4.6. Prior and Concomitant Medications

Medications taken by subjects prior to starting the study will be summarized. These include medications for JIA such as MTX, other DMARDs, oral corticosteroids, and NSAIDs.

Concomitant medications will be summarized through Week 28, 52 and 252 for all subjects who belong in the full analysis set.

5. EFFICACY

5.1. Analysis Specifications

5.1.1. Level of Significance

No statistical testing will be performed.

5.1.2. Data Handling Rules

No data handling rules will be applied to all individual endpoints and composite endpoints that are not dichotomous. Observed data will be summarized.

For a dichotomous composite endpoint, subjects who have completely missing data (ie, all components of the composite endpoint are missing) will be assumed to be a non-responder. When at least 1 of the components is non-missing, last observation carried forward (LOCF) will be used for imputing the components with missing data.

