Rationale: With approximately half the planned number of subjects enrolled in the study to date, the study population exhibits a range of C-reactive protein (CRP) levels that would support the planned population pharmacokinetics (PK) analysis. At the same time, the Sponsor has received consistent feedback from the Steering Committee and investigators that otherwise qualified subjects have failed screening because their CRP was<0.1 mg/dL. Given these facts, the inclusion criterion has been revised to allow approximately 30% of the study population to have a screening CRP of <0.1 mg/dL in order to enhance enrollment in the study without affecting the Sponsor's ability to fulfill the objectives of the study.

| Synopsis, Objectives | The primary objective of this study is to assess the pharmacokinetics (PK) following intravenously administered golimumab in subjects (ages 2 to less than 18 years) with pJIA manifested by ≥ 5 joints with active arthritis and C reactive protein (CRP) of ≥ 0.1 mg/dL despite methotrexate (MTX) therapy for ≥ 2 months. |
|---------------------------------|---|
| Synopsis, Subject Population | Subjects must have ≥ 5 joints with active arthritis as defined by American College of Rheumatology (ACR) criteria at screening and enrollment. and must have a screening CRP of ≥ 0.1 mg/dL. |
| 2.1 Objectives | The primary objective of this study is to assess the PK following intravenously administered golimumab in subjects (ages 2 to less than 18 years) with pJIA manifested by ≥ 5 joints with active arthritis-and CRP of ≥ 0.1 mg/dL despite MTX therapy for ≥ 2 months. |
| 4.1 Inclusion Criteria | 6. Subjects must have a screening CRP of ≥0.1 mg/dL with the exception of |

approximately 30% of the study population.

Rationale: Text has been revised to clarify the appropriate MTX dose for subjects according to their body surface.

| Kat | ionaie: | Text has been | revised to clarify | tne appropriate | MITA dose to | or subjects accord | ling to their boo | ay surrace |
|------|---------|---------------|--------------------|-----------------|--------------|--------------------|-------------------|------------|
| area | (BSA) | measurement. | | | | | | |

| Synopsis, Overview | Commercial MTX is to be administered at a stable dose of 10-30 mg/m²/week in subjects |
|--------------------|---|
| of Study Design | with BSA <1.67 m ² or a stable minimum dose of 15 mg/week in subjects with BSA |

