Evaluations should be performed at least every 6 months in all subjects. Subjects who test ANA positive at screening will be required to undergo slit lamp evaluation by a qualified ophthalmologist to evaluate for subclinical uveitis in the screening period, before first study drug administration as well as at least every 3 months subsequent.

Footnote i

To be completed by the parent or caregiver, preferably the same parent or caregiver should complete at every visit. Subjects who are emancipated juveniles (ages 15 to <18 years) at study entry may complete the assessments themselves. **Ideally** the same individual (eg, parent, caregiver, or subject) who completes the assessments at the start of the study should complete the assessments throughout the study, at least

| Applicable Section(s) | Description of Change(s) |
|--|--|
| Footnote j | All visit-specific PRO assessments should be conducted before any tests, procedures, or other consultations for that visit to prevent influencing subjects' perceptions. |
| | Parent/subject assessment of overall well-being has been deleted |
| | Visual analog scale for pain has been deleted |
| | CHQ assessments have been deleted. |
| | Checks for the following assessments during the screening period have been deleted: Parent/subject assessment of overall well-being, Physician Global Assessment of disease activity, and Visual analog scale for pain |
| Table 2: From Week 60 Through Week 156 (Long-term Extension) | JADAS assessment has been added at Weeks 68, 84, 100, 116, 132, and 148. |
| | Antibodies to golimumab assessments have been added at Weeks 4 and 8 |
| | QuantiFERON TB Gold test was deleted at Weeks 60 and 108 and has been added at Weeks 100 and 148. |
| | Uveitis evaluations were deleted at Weeks 76, 100, 124, and 148 and added to Weeks 68, 92, 116, and 140. |
| Footnote b | Includes skin exam and Tanner staging every 6 months. |
| Footnote e | Evaluations should be performed at least every 6 months in all subjects. Subjects who test ANA positive at screening will be required to undergo slit lamp evaluation by a qualified ophthalmologist at least every 3 months. |

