| Footnote h | To be completed by the parent or caregiver, preferably the same parent or caregiver should complete at every visit. Subjects who are emancipated juveniles (ages 15 to <18 years) at study entry may complete the assessments themselves. Ideally the same individual (eg, parent, caregiver, or subject) who completes the assessments at the start of the study should complete the assessments throughout the study. |
| Footnote i | All visit-specific PRO assessments should be conducted before any tests, procedures, or other consultations for that visit to prevent influencing subjects' perceptions. |
| | Parent/subject assessment of overall well-being has been deleted |
| | Visual analog scale for pain has been deleted |
| | CHQ assessments have been deleted. |
| | |

| JADAS assessment has been added at Weeks 164, 180, 196, 212, 228, and 244. | | | | | | | |
|--|--|--|--|--|--|--|--|
| dies to golimumab assessments have been added at Weeks 4 and 8 | | | | | | | |
| FERON TB Gold test was deleted at Week 172 and has been added at Week 196 | | | | | | | |
| evaluations were deleted at Weeks 172, 196, 220, and 244 and added to Weeks 38, 212, 236, and 252. | | | | | | | |
| es skin exam and Tanner staging every 6 months. | | | | | | | |
| tions should be performed at least every 6 months in all subjects. Subjects who NA positive at screening will be required to undergo slit lamp evaluation by a ed ophthalmologist at least every 3 months. | | | | | | | |
| completed by the parent or caregiver, preferably the same parent or caregiver complete at every visit. Subjects who are emancipated juveniles (ages 15 to <18 at study entry may complete the assessments themselves. Ideally the same ual (eg, parent, caregiver, or subject) who completes the assessments at the start study should complete the assessments throughout the study. | | | | | | | |
| sit-specific PRO assessments should be conducted before any tests, lures, or other consultations for that visit to prevent influencing subjects' tions. | | | | | | | |
| subject assessment of overall well-being has been deleted | | | | | | | |
| analog scale for pain has been deleted | | | | | | | |
| ssessments have been deleted. | | | | | | | |
| | | | | | | | |

Description of Change(s)

Rationale: Revisions were made to several sections of the synopsis to reflect the changes made in the protocol

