9.2. Efficacy

9.2.1. Evaluations

The Time and Events Schedule summarizes the frequency and timing of efficacy measurements applicable to this study (Table 1). After Week 52, investigators will complete an attestation form annually to document that the subject is benefiting from treatment.

9.2.1.1. **Joint Evaluation**

Each of 75 joints will be evaluated for tenderness, and 68 joints will be evaluated for swelling and pain and limitation on motion according to the standard PRINTO/PRCSG joint evaluation. A consistent joint assessor, with at least 1 year of experience in performing joint assessment, will be designated at each study center to perform all joint assessments.

Training will be provided to a single consistent joint assessor from each site before the start of subject enrollment; the training is mandatory unless the site's joint assessor has taken certified training provided by PRINTO or PRCSG. If a consistent joint assessor was trained by the Sponsor in a previous clinical study, he or she may receive a waiver for this training. Documentation of Sponsor or PRINTO/PRCSG training will be maintained in the Trial Center File. If possible, the consistent joint assessor for the study should not be changed during the study. However, the assessor from each site who attends the consistent joint assessor training provided by the Sponsor may train 1 additional assessor at the site for coverage during their absences.

It is expected that any additional consistent joint assessors who are trained will also have 1 or more years of experience as joint assessors or be approved by the Sponsor. If the designated consistent joint assessor from the site trains any additional assessors at the site, a letter documenting the training should be filed in the site's Trial Center File. In addition, if more than 1 consistent joint assessor at a site performs joint assessments during the study, the names of all consistent joint assessors performing the joint evaluation at the site at each visit must be listed in the Trial Center File and documented in the source document.

It is preferable that the consistent joint assessor who performs the baseline joint assessments for a subject also performs the joint assessments for that subject for all subsequent visits through the final efficacy assessment at Week 52.

Nonevaluable Joints

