 - TB and/or a positive QuantiFERON®-TB Gold test result (or a positive tuberculin skin test result in countries in which the QuantiFERON®-TB Gold test is not approved/registered or the tuberculin skin test is mandated by local Health Authorities), unless active TB can be ruled out and appropriate treatment for latent TB can be initiated prior to the next administration of study agent and continued to completion. Indeterminate QuantiFERON®-TB Gold test results should be handled as in Section 9.1.2. Subjects with persistently indeterminate QuantiFERON®-TB Gold test results may continue without treatment for latent TB if active TB is ruled out, their chest radiograph shows no abnormality suggestive of TB (active or old, inactive TB) and the subject has no additional risk factors for TB as determined by the investigator. This determination must be promptly reported to the Sponsor's medical monitor and recorded in the subject's source documents and initialed by the investigator.
 - A subject receiving treatment for latent TB discontinues this treatment prematurely or is noncompliant with the therapy.

All subjects who discontinue study agent infusions during the study will be followed for approximately 8 weeks after the last infusion is administered.

Note: The visit that is approximately 8 weeks after the last study agent infusions is referred to as the "final safety follow-up visit," which may occur at a scheduled or an unscheduled visit.

Subjects who discontinue study agent infusions but do not terminate study participation will have the following assessments performed at the final safety follow-up visit:

- Safety evaluation including AE review, TB evaluation, and the collection of a blood sample for routine laboratory analyses, determination of the presence of ANA/anti-double-stranded deoxyribonucleic acid (dsDNA) antibodies, and antibodies to golimumab; after Week 52, other safety evaluations are performed at the discretion of the investigator (vital signs, review of systems, uveitis evaluation).
- Concomitant medication review (after Week 52, medications should be reviewed and documented in subject's source records; medications used to treat or associated with AEs and SAEs should be recorded in the source document as well as the CRF).
- Efficacy evaluations (joint assessments, JIA assessments, and collection of blood sample for CRP) through Week 52 only.

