2.3.2. Full Analysis Set

The full analysis set includes all enrolled subjects who received at least 1 infusion.

This analysis set will be used for efficacy analysis and safety analysis, unless otherwise specified.

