5.4.2. Analysis Methods

Unless otherwise specified, the analysis population will be the full analyses set defined in Section 2.3.2.

Summaries over time will be for all visits data was collected through Week 28, 52, and 252, if the visit of the endpoint is not specified. Simple descriptive summary statistics, such as n, mean, SD, median, IQ range, minimum, and maximum for continuous variables, and counts and percentages for discrete variables will be used to summarize most data.

The following endpoints will be summarized over time.

- 1. The proportion of subjects who are JIA ACR 30, 50, 70, and 90 responders
- 2. The proportion of subjects who have inactive disease
- 3. The proportion of subjects in clinical remission on medication for pJIA
- 4. The improvement from baseline in the JIA ACR core set of components
- 5. The proportions of subjects who are JIA ACR 30, 50, 70, and 90 responders by disease subtype, and/or age through Week 52
- 6. The change from baseline in CHAQ
- 7. CRP concentrations
- 8. The change from baseline in JADAS 10, 27, and 71 scores
- 9. The proportion of subjects who achieve JADAS 10, 27, and 71 minimal disease activity

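### The SAP scores long-term extension visits as non-response for children whose efficacy assessments Amendment 4 removed by design

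*SAP*

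**What the plan says.** Three SAP provisions act together.

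- **Missing-data rule (SAP 5.1.2).** For a dichotomous composite, "subjects who have completely missing data (ie, all components of the composite endpoint are missing) will be assumed to be a non-responder". If at least one component is present, the missing ones are filled by LOCF. Nothing is said about assessments the protocol no longer requires.
- **Denominator (SAP 2.3.2).** The full analysis set is all enrolled subjects with at least one infusion: "This analysis set will be used for efficacy analysis and safety analysis, unless otherwise specified".
- **Visits (SAP 5.4.2).** "Summaries over time will be for all visits data was collected through Week 28, 52, and 252".

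The current protocol (Amendment 4) has no efficacy measurement after Week 52. Section 9.2.1.1 refers to the "final efficacy assessment at Week 52". Section 10.2 lists, for the final safety follow-up visit, "Efficacy evaluations (joint assessments, JIA assessments, and collection of blood sample for CRP) through Week 52 only". In the Time and Events Schedules, Tables 2 and 3 keep only an annual attestation form under Efficacy.

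**The concern.** The SAP wording selects visits, not subjects. An LTE visit with no efficacy data from anyone drops out of the summary. A visit with data from some subjects stays in and keeps the whole full analysis set as its denominator. Anyone without data at that visit is then a non-responder, whether the child dropped out, missed the visit, or attended after the sponsor had cancelled the assessment.

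Long-term response would therefore appear to fall because of a protocol change and not because benefit was lost, and the fall would follow enrolment date. A child whose investigator attests every year to continuing benefit could be tabulated as a failure. Continuous measures use observed data, so LTE means and LTE responder rates would also rest on different denominators.

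**Working it through.** The plan states no figure for this point, so there is none to reproduce. The check has three parts.

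**1. Were LTE efficacy visits ever scheduled, and when?** The amendment log is used here only as history. For Amendment 1 it records "JADAS assessment has been added at Weeks 68, 84, 100, 116, 132, and 148" and "JADAS assessment has been added at Weeks 164, 180, 196, 212, 228, and 244", which is every 16 weeks from Week 68 to Week 244. Amendment 2 took JADAS off the schedules as a separate line because it is a calculation. The superseded wording of Section 3.1.3, shown in the Amendment 4 log, confirms that disease activity was still recorded every 16 weeks in the LTE.

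**2. Would those visits be partly populated?** The Amendment 3 rationale (28 February 2017) begins "With approximately half the planned number of subjects enrolled in the study to date".

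- 28 February 2017 to 16 December 2019 = 1021 days; 1021 / 7 = 145.9 weeks.
- Latest enrolment date that allows a visit to be reached first = effective date − visit week.

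| Amendment takes effect | Visit | Enrolled no later than |
|---|---|---|
| 16 Dec 2019 (issue date) | Week 68 | 27 Aug 2018 |
| | Week 100 | 15 Jan 2018 |
| | Week 132 | 5 Jun 2017 |
| | Week 148 | 13 Feb 2017 |
| | Week 244 | 13 Apr 2015 |
| 6 Apr 2020 (16 weeks later) | Week 164 | 13 Feb 2017 |
| 27 Jul 2020 (32 weeks later) | Week 180 | 13 Feb 2017 |

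The lags of 0, 16 and 32 weeks are assumptions. Protocol 17.1 requires ethics approval before an amendment is implemented, so sites would differ. With about half of 120 subjects enrolled by 28 February 2017, about 60 or fewer could have data at Week 148 (no lag), Week 164 (16 weeks) or Week 180 (32 weeks), and fewer at later visits. So f could be about 50% or more from there on, and smaller at earlier LTE visits.

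**3. What does the rule then report?** Let p be the response rate among those assessed. Reported rate = p × (1 − f). For illustration, p = 87.3%, the Week 16 JIA ACR 30 rate in the earlier subcutaneous study (Protocol 1.1.2.2).

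| | f = 25% | f = 50% |
|---|---|---|
| No dropout | 0.873 × 0.75 = 65.5% | 0.873 × 0.50 = 43.7% |
| 20 of 120 dropouts scored first: 0.873 × 100/120 = 72.8% | 72.8% × 0.75 = 54.6% | 72.8% × 0.50 = 36.4% |

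At f = 50% without dropout, p = 60% gives 30.0% and p = 95% gives 47.5%.

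**Which endpoints.** JIA ACR 30/50/70/90 and minimal disease activity lose every component after Week 52, so the rule bites in full. For inactive disease, physical examination continues and uveitis evaluation is discretionary. A component may therefore be present, and LOCF would carry old values forward. Clinical remission (SAP 5.4.1.3) counts only visits that were not missed. The direction is uncertain for these two.

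**A separate point, older than Amendment 4.** SAP 7.3 plans JIA ACR 30 by antibody status at Weeks 28, 52 and 252. Antibody sampling ends at Week 244 (Protocol 9.3.4), and Week 252 was not among the earlier LTE efficacy visits.

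**The case against.** The strongest reply is that the SAP matched the protocol in force when it was written, and that a later version may exist. The April 2020 COVID-19 Appendix says further analyses will be set out in the SAP(s), and the supplied SAP contains none. That stands: a later SAP that deals with this closes the point.

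It can also be argued that an assessment never required is not missing, and that the reference to visits with collected data could be read per subject. The text does not support this. Section 5.1.2 makes no exception, Section 5.4.2 names visits and fixes the population as the full analysis set, and the wording on missed visits covers remission only.

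The consequence is limited. No hypothesis is tested, there is no primary or major secondary efficacy endpoint, and LTE rates in a single-arm, open-label study with optional LTE entry and free changes of background therapy are hard to interpret anyway. That is a fair reason to rank the point below anything touching the PK endpoints, but not to leave in a rule that gives a wrong number.

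The size is illustrative: there is no enrolment curve, enrolment end date or site implementation date, and 87.3% comes from another route and an earlier time point. If enrolment ended before the cut-offs for the early LTE visits, f there is zero. The ±1-week visit window moves the Week 148 cut-off only from 13 to about 20 February 2017. Finally, the Week 252 label in SAP 7.3 may mean the database lock and not the visit. It is a separate point and adds no weight to the main one.

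**Conclusion.** The concern holds: the rule is wrong as written for the current protocol. Followed literally, it counts children still on treatment as JIA ACR and minimal disease activity failures at partly populated LTE visits, solely because the assessment was withdrawn. The bias is downward by a factor of (1 − f). A halving from roughly Weeks 148–180 onward is plausible on the documents' dates, but it is not established. It rests on about half of subjects being enrolled by February 2017 and on an assumed implementation lag of 0 to 32 weeks. The percentages shown also assume p = 87.3%.

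Only descriptive responder proportions after Week 52 are affected. The point should be fixed before the Week 252 analysis.

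**What to change.** - Amend SAP 5.1.2 and 5.4.2 so that dichotomous composite summaries on the full analysis set stop at Week 52.
- If LTE visits are shown, limit each denominator to subjects whose visit date fell, or would have fallen, before Amendment 4 took effect at their site. Include those who had discontinued, and apply non-response only within that group, so that true dropouts still count as non-responders.
- In SAP 7.3, remove the Week 252 analysis of JIA ACR 30 by antibody status, leaving Weeks 28 and 52.
- If a later SAP version already does this, cite it.

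The cost is a short SAP amendment, some programming, and a list of the amendment's effective date by site. No further data are needed from subjects. LTE efficacy would be reported on fewer subjects, all of them earlier enrollees, and the tables should say so.
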